3.4 Investigational Medicinal Product

3.4.1 Dosage form and strengths

Investigational Product	Dosage form, strength
Tenalisib	Tablets; 200 mg and 400 mg.

Note: Please refer current Investigator's brochure for additional information of Tenalisib.

In case of roll over from the combination study, the combination agent (e.g. romidepsin) will be administered as part of SOC and will not be supplied/provided by Rhizen Pharmaceuticals SA.

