3.4.3 Preparation and administration of Investigational Products

At each visit, patients will be dispensed sufficient quantity of Tenalisib until the next visit. Study drug compliance will be reviewed with the patient at the beginning of cycle. Study drug compliance will be documented, including missed doses.

Guidelines for administration of Tenalisib:

- Method of administration: Tenalisib will be administered orally twice daily
- Pre-medications: None. No routine prophylactic anti-emetics or pre-medications will be given outside of protocol requirements. However, these medications may be administered for treatment of symptoms/adverse events.
- Tenalisib tablets will be self-administered orally twice daily one hour before a major meal (e.g. breakfast and dinner). Patients should not consume food during this one-hour period. ***Please note, patients will continue to receive the same dose they were receiving in previous protocols. (e.g. If patient is receiving Tenalisib 400 mg BID while rolling over, he/she will continue to receive 400 mg BID dose in compassionate study protocol).***
- Tenalisib tablets should be taken at approximately same time each day. Tablets should be swallowed; and should NOT be crushed or chewed.
- If a dose of Tenalisib is missed, it should be taken as soon as possible on same day with an interval of 8 hrs between two doses. If it is missed for the entire day, it should not be repeated. If vomiting occurs, no attempt should be made to replace the vomited dose.
- Study drug compliance should be reviewed with the patient at the beginning of cycle. Missed doses should be documented.

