7.5 Dose Modifications

The dose modification should be performed for the drug toxicity or underlying disease conditions. Guidelines (Refer [Table 2](#) and [3](#)) are intended to be applied when the investigator determines the event related to Tenalisib. Please note the dose modifications provided below should be used as a guidance and should be determined as per PI's clinical judgement.

Patients may resume Tenalisib, provided that the toxicity has resolved to Grade ≤ 2 or baseline and there is no clinical or radiographic evidence of disease progression. If study drug is delayed > 2 weeks because of an adverse event, strategy of re-initiation of study drug should be discussed with medical monitor.

At the discretion of the Investigator, a dose re-escalation may be permitted for patients who previously had a dose reduction. Holidays from study drug are discouraged. Any patient in whom similar toxicity recurs at the reduced dose should be discontinued from further Tenalisib treatment. Note: In exceptional case, a patient may be allowed following a careful assessment of benefit and risk by the investigator and with approval from the medical monitor.

Table 2: Dose Modifications for Hematologic Toxicity

Worst CTCAE Grade Toxicity	Action to be Taken
HEMATOLOGIC	
Neutropenia (ANC)	
Grade 3 $1.0 \times 10^9 / L < ANC \geq 0.5 \times 10^9 / L$	Maintain dose level. Monitor ANC at least weekly.
Grade 4 $0.5 \times 10^9 / L < ANC$	First incidence: Withhold* dose until resolved to \leq Grade 2 or baseline. Monitor ANC at least weekly. Resume treatment at the same dose level. Subsequent occurrence: Hold dose until resolved to \leq Grade 2 or baseline. Consider growth factor support. Resume treatment at the reduced dose level (Tenalisib 400 mg BID) if warranted.
Grade 3 Febrile neutropenia $ANC < 1000 / mm^3$ with a single temperature of $> 38.3^{\circ}C (101^{\circ}F)$	Withhold* dose until resolved to \leq Grade 2 or baseline, consider growth factor support, then reduce by 1 dose level (Tenalisib 400 mg BID), if

or a sustained temperature of $\geq 38^{\circ}\text{C}$ (100.4°F) for more than one hour.	warranted. If the ANC is $<1 \times 10^9/\text{L}$ ($1000/\mu\text{L}$) before therapy, the dose shall not be modified as long as $\text{ANC} > 0.5 \times 10^9/\text{L}$.
Thrombocytopenia	
Grade 3 thrombocytopenia with Grade 1 bleeding	Maintain Tenalisib dose. Monitor platelet count at least weekly.

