Hepatic*	
Transaminitis
 
Grade 1-2 Transaminitis (ALT/AST $>1-3 \times \text{ULN}$ if baseline is normal; $1.5 - 3 \times \text{baseline}$ if baseline is abnormal):
 
 Maintain Tenalisib dose and initiate prednisone 40 mg daily. Monitor AST/ALT weekly until resolved and then taper steroid. Withhold Tenalisib in case of development of grade 2 transaminitis or worsening of Grade 1 transaminitis while on steroids. 
Grade 3 Transaminitis ($\text{ALT/AST} >5-20 \times \text{ULN}$; $>5-20 \times \text{baseline}$ if baseline is abnormal):
 
 Withhold Tenalisib and monitor ALT/AST twice a weekly until Grade ≤ 1; restart Tenalisib at one dose lower (Tenalisib 400 mg BID). Initiate prednisone 1 mg/kg in case no improvement after withholding Tenalisib for 1 week. Monitor ALT/AST twice a weekly until Grade ≤ 1; restart Tenalisib at one dose lower (Tenalisib 400 mg BID). and taper steroid. If no immediate response to steroids within 7 days, initiate mycophenolate mofetil. In case of recurrence of transaminitis at reduced doses, discontinue Tenalisib permanently after assessing risk versus benefit. 
Grade 4 Transaminitis ($\text{ALT/AST} >20 \times \text{ULN}$; $>20 \times \text{baseline}$ if baseline is abnormal):
 
 Tenalisib should be permanently discontinued. 
Bilirubin:
 
 Grade 2 ($> 1.5-3 \times \text{ULN}$; $>1.5- 3 \times \text{baseline}$ if baseline is abnormal): Maintain Tenalisib dose. Monitor at least weekly until $\leq 1 \times \text{ULN}$

	
 • Grade 3 ($> 3-10 \times \text{ULN}$; $> 3 - 10 \times \text{baseline}$ if baseline is abnormal): Withhold Tenalisib. Monitor at least weekly until bilirubin is $\leq 1 \times \text{ULN}$; Restart Tenalisib at one dose lower (Tenalisib 400 mg BID). • Grade 4 ($> 10 \times \text{ULN}$; $> 10 \times \text{baseline}$ if baseline is abnormal): Discontinue Tenalisib permanently
Infection	
Grade 3 or higher sepsis or pneumonia
 
 • Withhold Tenalisib until infection has resolved. • Restart at the same or at the reduced dose (Tenalisib 400 mg BID)

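### For a patient on 400 mg BID, five Table 3 entries call for a dose reduction but print 400 mg BID, and no lower level is given

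*Combined protocol and SAP*

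**What the plan says.** On the entry dose, Section 3.4.3 gives this example: "If patient is receiving Tenalisib 400 mg BID while rolling over, he/she will continue to receive 400 mg BID dose in compassionate study protocol". The strengths listed in Section 3.4.1 are "Tablets; 200 mg and 400 mg", with no ladder of dose levels there or elsewhere.

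On reductions, Table 3 in Section 7.5 says for Grade 3 transaminitis: "restart Tenalisib at one dose lower (Tenalisib 400 mg BID". The Grade 3 bilirubin entry has equivalent wording. Grade 3 rash, moderate diarrhoea that does not respond to antidiarrhoeals, and severe diarrhoea each restart at a reduced level that is again given as 400 mg BID. Table 2 is conditional, for example for repeated Grade 4 neutropenia: "Resume treatment at the reduced dose level (Tenalisib 400 mg BID) if warranted".

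The text of Section 7.5 adds three general provisions:

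- Status of the tables: "the dose modifications provided below should be used as a guidance", with the decision left to the investigator's clinical judgement.
- After a delay of more than 2 weeks for an adverse event: "strategy of re-initiation of study drug should be discussed with medical monitor".
- Recurrence: "Any patient in whom similar toxicity recurs at the reduced dose should be discontinued from further Tenalisib treatment". In exceptional cases "a patient may be allowed following a careful assessment of benefit and risk by the investigator and with approval from the medical monitor".

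**The concern.** The words of the entries call for a lower dose, but the figure in brackets is fixed and does not depend on the dose the patient is taking. For a patient on 400 mg BID the two contradict each other: once a related toxicity has resolved, the printed restart dose is the dose at which it occurred.

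This is a patient-safety matter. Section 3.4.5 lists raised ALT/AST and skin rash among the events reported with Tenalisib, and both are among the affected entries. Table 3 asks for monitoring until resolution. After restart, however, visits are every 3 months with no protocol-required safety laboratory tests (Section 6.3), and liver-enzyme monitoring is only recommended (Section 3.4.5). Detection of a second event would then rest largely on local practice.

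A second ambiguity follows. The stop-on-recurrence rules in the Section 7.5 text and the transaminitis entry apply at the reduced dose. A patient already reduced to 400 mg BID in the earlier study can reasonably be read as being at that dose. For a patient whose original dose was 400 mg BID, the protocol does not say.

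**Working it through.** **Entries in Section 7.5 that call for a lower dose**

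| Entry | Table | Dose printed | Alternative or condition in the entry |
|---|---|---|---|
| Grade 4 neutropenia, subsequent | 2 | 400 mg BID | if warranted |
| Grade 3 febrile neutropenia | 2 | 400 mg BID | if warranted |
| Thrombocytopenia, subsequent | 2 | 400 mg BID | if warranted |
| Grade 3 transaminitis (dose printed twice, counted once) | 3 | 400 mg BID | none |
| Grade 3 bilirubin | 3 | 400 mg BID | none |
| Grade 3 or higher sepsis or pneumonia | 3 | 400 mg BID | same dose also allowed |
| Grade 3 rash | 3 | 400 mg BID | none |
| Grade 2 pneumonitis | 3 | not named | resumption is optional |
| Moderate diarrhoea, unresponsive | 3 | 400 mg BID | none |
| Severe diarrhoea | 3 | 400 mg BID | none |
| Other Grade 3 | 3 | 400 mg BID | if warranted |
| Recurrence of other Grade 3 | 3 | not named | or discontinue |
| Other Grade 4 | 3 | 400 mg BID | or discontinue |

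**Counts**

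- Naming 400 mg BID: 3 (Table 2) + 8 (Table 3) = 11. No dose named: 2. Total: 11 + 2 = 13. Naming a level below 400 mg BID: 0.
- Among the 11: 5 with no alternative, 4 if warranted, 1 or discontinue, 1 same dose allowed; 5 + 4 + 1 + 1 = 11.
- Share with no alternative: 5/13 = 38%. Counting printed strings instead of entries gives 6 rather than 5, because transaminitis prints the dose twice.

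**Printed reduction** = (current dose − printed dose) / current dose

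- At 400 mg BID: (400 − 400)/400 = 0%.
- At 800 mg BID: (800 − 400)/800 = 50%. An 800 mg BID entry dose is an assumption; Section 7.4.2 mentions 800 mg twice a day only as an example in the overdose definition.

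**Stop on recurrence, for the 5 entries with no alternative**

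- Rash has its own rule that does not depend on dose: 1.
- Transaminitis has a rule tied to reduced doses: 1.
- Bilirubin and the two diarrhoea entries have only the general Section 7.5 rule, tied to the reduced dose: 3.
- Entries that depend on what reduced dose means: 1 + 3 = 4 of 5.

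**Length of hold** (2 weeks = 14 days)

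- Up to 14 days: no required discussion.
- More than 14 and up to 28 days: discussion with the medical monitor.
- More than 28 days: permanent stop unless the medical monitor approves. In Table 3 the asterisk for this footnote stands only on the hepatic heading, so its reach to rash and diarrhoea is not explicit.

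**Second route to the same gap.** A patient reduced to 400 mg BID in this study for one toxicity may later have a different one. The table again prints 400 mg BID, and the recurrence rule does not apply because it covers only similar toxicity.

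**The case against.** The strongest reply is that no careful investigator would read one dose lower as an order to restart at the same dose. Every entry is guidance subject to clinical judgement, a real reduction is plainly intended and a 200 mg tablet exists. This stands as a limit on the likely harm. It does not tell sites whether to choose 200 mg BID, stop, or accept the printed 400 mg BID. Section 3.4.1 lists 200 mg as a tablet strength and does not establish 200 mg BID as a treatment dose.

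It can also be said that the tables themselves label 400 mg BID as the reduced level, so recurrence at 400 mg BID already triggers the stop. With the 800 mg example in Section 7.4.2, many 400 mg BID entrants may have been reduced before. That reading is reasonable for patients reduced earlier, and the parent-protocol doses are not available to test how many there are. It does not cover the first event of a new toxicity, and it remains uncertain for a patient who started at 400 mg BID.

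Other protections have no time threshold: withdrawal for related Grade 3/4 non-hematological toxicity in the investigator's opinion (Section 4.3), advice from the medical monitor (Section 12.3) and the recovery conditions before restart. The most dangerous events need no dose level because the drug is stopped: Grade 4 transaminitis or bilirubin, SJS/TEN/DRESS, Grade 3 or life-threatening pneumonitis, and life-threatening diarrhoea. All of this is true, and none of it gives a restart level below 400 mg BID.

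Finally, 38% counts table entries and does not measure risk, and the affected number could be zero. Both points are correct.

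**Conclusion.** The concern holds and should be fixed. For a patient the protocol itself gives as an example, 5 of 13 dose-reduction entries require a reduction and print none (0%). Five further entries do the same conditionally: 4 if a reduction is judged warranted and 1 unless the drug is stopped. The infection entry allows the same dose and is not counted against the plan. No level below 400 mg BID appears anywhere, and 4 of the 5 entries with no alternative rely on a recurrence rule whose key term is undefined for a patient whose original dose was 400 mg BID.

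The count rests on the two tables alone. The number of patients exposed is unknown, from 0 to about 50 (the approximate planned enrolment). Endpoints and analysis are not affected.

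**What to change.** 1. In Tables 2 and 3, replace the fixed 400 mg BID with one level below the dose at onset of the event. This also covers a patient reduced during this study who then has a different toxicity.
2. Add a short dose-level table covering every entry dose. Below 400 mg BID it should state either 200 mg BID or permanent discontinuation; the clinical team should choose.
3. Refer the Grade 2 pneumonitis and recurrent other Grade 3 entries to the same table.
4. State whether a patient who entered at 400 mg BID counts as being at the reduced dose for the recurrence rules in the Section 7.5 text and the transaminitis entry. Treat separately those reduced in the earlier study and those whose original dose was 400 mg BID.

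The cost is protocol wording and one table, made through an amendment with IRB/IEC approval (Section 11.1). Re-consent is needed only if the change is judged to alter the design or risks substantially (Section 10.5). Sample size, visits and endpoints do not change.

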8 ASSESSMENT OF EFFICACY

Efficacy evaluations will be performed at the physician's discretion as part of standard of care (SOC). These evaluations (e.g. measurement of lymph node, mSWAT) will not be reported in CRF, however the date of disease progression will be reported.

9 STATISTICAL METHOD AND CONSIDERATIONS

The primary purpose of this study is to offer patients who completed a Rhizen sponsored clinical study without progression the opportunity to continue to receive Tenalisib on a compassion basis. The safety and progression status will be summarized as appropriate. No formal sample is determined for this study and final sample size will depend on the number of patients who benefitted and completed the Tenalisib study.

10 ETHICAL, FINANCIAL, AND REGULATORY CONSIDERATIONS

This trial will be conducted according to the standards of Good Clinical Practice outlined in the ICH E6 Tripartite Guideline, and CFR Title 21 part 312, World Medical Association's Declaration of Helsinki, applicable government regulations, institutional research policies and procedures and any other local applicable regulatory requirement(s).

All potential serious breaches must be reported to Rhizen immediately. A serious breach is a breach of the conditions and principles of GCP in connection with the study or the protocol, which is likely to affect, to a significant degree, the safety or physical or mental integrity of the subjects of the study or the scientific value of the study.

10.1 IRB/IEC Approval

The trial documents (e.g, protocol, ICF, IB, available safety information, patient documents, patient recruitment procedures, information about payments (i.e., PI payments) and compensation available to the patients and documentation evidencing the PI's qualifications) should be submitted to the IRB/IEC for ethical review and approval if required by local regulations, prior to the trial start.

The PI/Rhizen and/or designee will follow all necessary regulations to ensure appropriate, initial, and ongoing, IRB/IEC trial review. The PI/Rhizen (as appropriate) must submit and, where necessary, obtain approval from the IRB/IEC for all subsequent protocol amendments and changes to the informed consent document. Investigators will be advised by Rhizen/designee whether an amendment is considered substantial or non-substantial and whether it requires submission for approval or notification only to an IRB/IEC.

10.2 Regulatory Approval

As required by local regulations, Rhizen will ensure all legal aspects are covered, and approval of the appropriate regulatory bodies obtained, prior to trial initiation. If required, Rhizen will also ensure that the implementation of substantial amendment to the protocol and other relevant trial documents happen only after approval by the relevant regulatory authorities.

10.3 Insurance and Indemnity

Details of insurance and/or indemnity will be contained within the written agreement between the PI or site and Rhizen. Rhizen will reimburse the subject for all study-related injuries provided that the injury does not arise from the subject's misuse of the study drug or failure to follow the Investigator's instructions.

10.4 Financial Disclosure and Obligations

Principal Investigators and Sub-Investigators are required to provide financial disclosure information to allow Rhizen to submit the complete and accurate certification or disclosure statements required under Part 54 of Title 21 of the CFR. In addition, the Principal Investigator/Sub- Investigators must provide to the Sponsor a commitment to promptly update this information if any relevant changes occur during the course of the investigation and for 1 year following the completion of the study.

10.5 Informed Consent

The informed consent form will be submitted for approval to the IRB/IEC that is responsible for review and approval of the trial. Each consent form must include all of the relevant elements currently required by the US FDA or state regulations and national requirements. Translation of the informed consent form is allowed if necessary.

Before recruitment and enrollment into the trial, each prospective candidate will be given a full explanation of the trial. Once the essential information has been provided to the prospective candidate, and the investigator is sure that the individual candidate understands the implications of participating in this trial, the candidate will be asked to give consent to participate in the trial by signing an informed consent form. A notation that written informed consent has been obtained will

be made in the patient's medical record. A copy of the signed informed consent form will be provided by the investigator to the patient.

If an amendment to the protocol substantially alters the trial design or the potential risks to the patients, the patient's re-consent to continue participation in the trial should be obtained.

10.6 Confidentiality

10.6.1 Patient confidentiality

Confidentiality of patient's personal data will be protected in accordance with the Health Insurance Portability and Accountability Act of 1996 (HIPAA) and national data protection laws, as applicable. HIPAA regulations require that, in order to participate in the trial, a patient must sign an authorization from the trial that he or she has been informed of following:

- a. What protected health information (PHI) will be collected from patients in this trial;
- b. Who will have access to that information and why;
- c. Who will use or disclose that information;
- d. The information collected about the research trial will be kept separate from the patient's medical records, but the patient will be able to obtain the research records after the conclusion of the trial;
- e. Whether the authorization contains an expiration date;
- f. The rights of a research patient to revoke his or her authorization.

In the event that a patient revokes authorization to collect or use his or her PHI, the investigator, by regulation, retains the ability to use all information collected prior to the revocation of patient authorization. For patients that have revoked authorization to collect or use PHI, attempts should be made to obtain permission to collect at least vital status (i.e., that the patient is alive) at the end of their scheduled trial period.

In compliance with ICH GCP guidelines and applicable parts of 21 CFR, it is a requirement that the investigator and institution permit authorized representatives of Sponsor, the regulatory authorities and the IRB/IEC direct access to review the patient's original medical records at the site for verification of trial-related procedures and data.

Measures to protect confidentiality include- only a unique trial number and initials will identify patients on CRF, or other documents submitted to Rhizen. This information, together with the patient's date of birth, will be used in the database for patient identification. Patient names or addresses will not be entered in the CRF or database. No material bearing a patient's name will be kept on file by Sponsor. Patients will be informed of their rights within the ICF. Therefore, absolute confidentiality cannot be guaranteed.

10.6.2 Investigator's responsibilities

Medical supervision is the responsibility of the Principal Investigator named on the FDA Form 1572. The Investigator may delegate day-to-day activities to a sub-investigator listed on these forms but retains overall responsibility for ensuring that the study is conducted properly and in accordance with the study protocol. The Investigator is required to provide the Sponsor with his/her own CV and applicable licensure, as well as those of the personnel assuming significant responsibility in the study (e.g., sub-investigators). The Investigator is responsible for ensuring

that the study is conducted according to applicable health authorities (FDA), sound medical practices, and in compliance with applicable regulations (21 CFR, ICH).

10.6.3 Investigator and Staff training

All Investigators and their study personnel will receive training regarding the study procedures and GCP/regulations specific to the conduct of clinical trials. This training will be documented and will take place prior to enrollment and throughout the study as necessary.

11 RECORD RETENTION AND DOCUMENTATION OF THE TRIAL

11.1 Amendments to the Protocol

If an amendment to the protocol is required, the amendment will be originated and documented by Rhizen. All amendments require review and approval of Rhizen. The written amendment must be submitted and approved by the IRB/IEC.

